### 5.5.2 Second session

The patient will come to the Hospital for primary impressions with alginate. Then a cast will be made with gypsum for study the case and bite of the patient will be taken with wax to record it.

### 5.5.3 Third session

The patient will come to the Hospital to operate the surgery within 15-20 days after having the study cast revised by a dentist and specialist from the fixed department. The patient will have a temporary prosthesis (Fixed or Removable) after the surgery of the implant. A periapical X-Ray will be taken immediately after the surgery to control the marginal bone loss. With respect to accepted criteria for the assessment of implant success were proposed by Albrektsson and colleagues (Albrektsson *et al.*, 1986), which to identify clinical evidence of successful osseointegration and survival of implants, suggested that a marginal bone loss of less than 1.5 mm in the first year and 0.2 mm in the following years is acceptable after implant loading.

### 5.5.4 Fourth session

Once the osseointegration time has elapsed, 3 months  $\pm$  15 days (in the mandible) and 4 months  $\pm$  15 days (in the maxilla), new clinical and radiographic measurements will be taken and then the rehabilitation phase will begin. The visits will be those corresponding to the required prosthetic treatment (fixed or removable), carried out according to the usual procedures and techniques of the prosthodontic service.

### 5.5.5 Fifth session

After placing the prosthesis on the patient, it will be reviewed every 3 months  $\pm$  15 days, for 2 years, to establish controls.

### 5.5.6 Sample's size calculation

Reference points for calculating marginal bone loss. Taken with permission from the author of [name]'s TFG. Red arrow, known mean of the implant. Green arrows reference the crestal bone and the marginal loss that occurred that allows us to compare at different times of the study.

### 5.6- Description of the treatment or intervention: drugs or techniques to be used.

- All patients will be anesthetized with 2% articaine with epinephrine,
- Regarding medication dispensed:
- Amoxicillin 1000 mg cps /8 hours for 7 days. (Patients allergic to Amoxicillin, we prescribe Clindamicina 600 mg cps /8H / 7 days).
- Dexketoprofeno 25 mg cps /8 hours for 7 days.
- Omperazol 25 mg cps / 8H/ 7 days for the stomach.
- As rescue medication: Paracetamol 1000 mg cps /8 hours for 7 days and/or Metamizol 650 mg cps 1/8 hours.
- Rinse with 0.12% chlorhexidine 2 times/7 days.

### 5.7.- Sample calculation

According to data obtained in the study by Natalia Palacios-Garzon et al, 2020 (taking into account that both are internally connected implants), in order to detect changes of 0.2mm we would need: Accepting an alpha risk of 0.05 and a beta risk of 0.2 in a bilateral contrast, 48 subjects (implants) in the first group and 48 (Implants) in the second are needed to detect a difference equal to or greater than 0.2 units.

The common standard deviation is assumed to be 0.34. A loss to follow-up rate of 5% has been estimated.

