## **2-JUSTIFICATION**

Various treatment protocols have been proposed to reduce marginal bone loss around implants, including placement of implants below the level of the bone crest (subcrestal placement). The supracrestal implant also has a positive impact on papilla formation and allows an emergence profile suitable for an aesthetic restoration. Allowing the implant-abutment interface to be in a position that contributes to bone remodeling in the implant neck region compared to implants placed at bone level (crestal placement). Marginal bone loss from implants placed bestially/subcrestally has shown conflicting results in recent studies. In this study we intend to evaluate bone loss in 100 Tissue level implants from two different commercial companies: Straumann bone level® with the Bio horizon Tissue level® implant. Buying the data obtained with the existing literature.

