## **5- MATERIAL AND METHOD**

### **5.1- Study design**

It is a prospective clinical study to compare two implants from two different brands of a similar design for their implantation [tissue level] and to evaluate the marginal bone loss of each dental implant in mm. 96 patients will be analyzed (an expected N of 48 per group, hoping to reach at least 100 implants per arm). See calculation of N in point 5.7.

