### **5.2- Study population**

The patients will be collected from patients who attend the master's degree in medicine, surgery and Oral Implantology, requesting implant-supported treatment. The study population will consist of patients who require treatment with dental implants, either partially or completely edentulous and who accept their placement and participation in the study. 4.2.1 Inclusion / exclusion criteria

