**5.5.- Procedures**

**5.5.1 First session and recruitment**

In this first session, before starting surgery and prosthodontic treatment, a thorough medical history will be taken. Each patient will be examined by extra-oral and intra-oral examination, in addition to the evaluation of their respective orthopantomography and cone beam computed tomography (CBCT), to evaluate the level of height and width of the bone for the placement of dental implants. This process will be carried out by the main researcher and supervised by another expert in Dentistry. Study participants who meet the inclusion criteria will then be recruited and asked if they wish to participate. Each of them will be given the following records.

If the patient meets the criteria and is interested, they will sign the informed consent and will be randomized using a randomization table of 10 in 10 implants [e.g.: randomization table ABBAABBBAB] to place one type or another of implant:

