### 5.8.- Statistical analysis

The variable data will be entered into the Excel program of the Microsoft Office 2019 Package (Microsoft Corporation, Washington, USA, 2013) and will be analyzed with the SPSS 26.0 program for Windows (SPSS, Illinois, USA, 2019).

The data collected will be processed using the STATA 14.0 statistical package. A descriptive analysis of the qualitative and quantitative variables will be carried out. The Kolmogorov-Smirnov test will be used to analyze the normality of the measurements.

The relationship between bone loss and implant position will be analyzed using parametric t-test.

The level of statistical significance chosen is 5% ( $\alpha = 0.05$ ). To evaluate the association between the dependent variable bone loss from T0 to T2 and successive Ts and the independent variables implant A, Implant B placement, a multiple linear regression analysis will be used.

All variables considered to potentially affect the study relationship, such as sex, age, and smoking, will be used as control variables in the regression; the number of cigarettes per day, maxilla or mandible, ISQ [implant stability value] and contact of the mesial and distal implant (penseic ade dinets and/or implants by mesial and distal)

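### The protocol sizes implants in 5.7, patients in 5.1 and allocates by a mixture in 5.5.1, and the brand regression in 5.8 has no patient term

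*Protocol*

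**What the plan says.** Five sections of the protocol bear on the unit.

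- **5.7 (sample calculation):** "48 subjects (implants) in the first group and 48 (Implants) in the second are needed" to detect 0.2 mm with a standard deviation of 0.34. The error rates are given as "Accepting an alpha risk of 0.05 and a beta risk of 0.2 in a bilateral contrast", and 5% loss to follow-up is assumed. Subject and implant are treated as the same thing.
- **5.1 (study design):** "96 patients will be analyzed (an expected N of 48 per group, hoping to reach at least 100 implants per arm", with a reference to 5.7 for the calculation. Here 48 counts patients, and the implants are additional.
- **2 (justification):** the aim is to "evaluate bone loss in 100 Tissue level implants from two different commercial companies". This can mean 100 in total or 100 of each brand.
- **5.5.1 (first session):** eligible patients who agree take part as follows: "they will sign the informed consent and will be randomized using a randomization table of 10 in 10 implants". The patient is randomised, but the table counts implants.
- **5.8 (statistical analysis):** for bone loss against "the independent variables implant A, Implant B placement, a multiple linear regression analysis will be used". The control variables include sex, age and smoking, and also "maxilla or mandible, ISQ [implant stability value] and contact of the mesial and distal implant". No term identifies the patient.

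Section 5.2 admits patients who are "either partially or completely edentulous", so the number of implants per patient will probably vary.

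**The concern.** The protocol does not settle what is counted, what is allocated and what is analysed. A team could stop at 96 implants or at 96 patients and claim to have met the plan either way, and the stated 80% power cannot be assigned to one design.

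The analysis raises the larger problem. Jaw, ISQ and neighbouring contact vary between implants in the same mouth, so the rows of the regression are most naturally implants. Two implants in one patient share the host, hygiene and smoking history, and their bone loss is likely to be correlated. If all implants of a patient are of one brand, as the two patient groups of 5.1 imply, ordinary regression treats these correlated values as independent. Its standard error for the brand effect is then too small, and a brand difference is declared too often.

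**Working it through.** **Inputs.** From 5.7: two-sided alpha 0.05, power 80%, difference 0.2 mm, SD 0.34, loss 5%. From 5.1: 48 patients and 100 implants per arm, so m = 100/48 = 2.083 implants per patient. The protocol gives no intra-patient correlation (ICC) and no variation in implants per patient (CV). The values used below are assumptions: ICC 0.1, 0.3 and 0.5, and CV 0 and 0.8.

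**1. The plan's own figure.** n = 2 × (1.960 + 0.842)² × 0.34² / 0.2² = 45.4 per arm, and 45.4/0.95 = 47.8, hence 48. It reproduces as a count of independent units, one value each. Nothing in it allows for several implants per patient.

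**2. Type I error of an implant-level analysis that ignores the patient, one brand per patient.** The design effect is DE = 1 + ((CV² + 1) × m − 1) × ICC, and the true two-sided error is 2 × (1 − Φ(1.96/√DE)).

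| ICC | DE, CV 0 | Error | DE, CV 0.8 | Error |
|---|---|---|---|---|
| 0.1 | 1.108 | 6.3% | 1.242 | 7.9% |
| 0.3 | 1.325 | 8.9% | 1.725 | 13.6% |
| 0.5 | 1.542 | 11.4% | 2.208 | 18.7% |

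**3. Power if 48 means patients.** Power = Φ(0.588 × √(n_eff/2) − 1.96), where 0.588 = 0.2/0.34. After 5% loss, 48 × 0.95 = 45.6 patients per arm remain.

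- One value per patient: n_eff = 45.6, power 80.2% (79.3% with the noncentral t distribution).
- Patient means, with 0.34 taken as the SD of a single implant and equal counts: n_eff = 45.6 × m / (1 + (m − 1) × ICC), power 94% at ICC 0.3 and 90% at ICC 0.5. At ICC 1 this returns to 80.2%, the floor.
- Implant-weighted analysis at ICC 0.5 and CV 0.8: n_eff = 95/2.208 = 43.0, power 78%.

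**4. Power if 48 means implants.** With 48 implants per arm at 2.08 per patient, equal counts and no loss, power is 78%, 71% and 64% at ICC 0.1, 0.3 and 0.5. After 5% loss it is 76%, 68% and 62%.

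**5. Simulation with unequal counts.** Per arm, 23, 12, 7 and 4 patients had 1, 2, 3 and 6 implants (46 patients, 92 implants, mean 2.0, CV 0.71). A t-test on implants stood in for the regression without covariates. There were 8,000 runs for error and 4,000 for power.

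| ICC | Error, implants | Error, patient means | Power, patient means |
|---|---|---|---|
| 0.3 | 11.7% | 4.8% | 88.4% |
| 0.5 | 16.1% | 4.8% | 85.3% |

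**The case against.** The best defence has four parts.

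- **The sample size is sound.** Section 5.1 gives a workable target of 48 patients per group, and extra implants can only help if the analysis respects the patient. This stands: the trial is not shown to be underpowered. Section 2 is background text and can be read as agreeing with 5.1, so it is an ambiguity rather than a proven conflict.
- **The inflated error depends on one brand per patient.** This also stands as a condition. Section 5.5.1 leaves open that a patient receives both brands. The error rates above would then not apply, and ignoring the patient could cost precision instead. The two patient groups of 5.1 nevertheless point to one brand per patient.
- **Clustering is commonly left to the analysis plan, and 5.8 never states what a row is.** This is less convincing. The protocol names the regression and its covariates, several of which belong to the implant. A later plan that added a patient term would be correcting a stated analysis, and it could not undo the conflict over what is sized and randomised.
- **The ICC is unknown, and 5.7 does not say whether 0.34 is the SD of a patient or of an implant.** Both are true. At ICC 0.1 the inflation is modest, 6% to 8%. If 0.34 is the SD of a single implant, patient means vary less, so quoting 80% for a patient-level comparison is conservative.

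**Conclusion.** The concern holds and must be fixed. Sections 5.1, 5.5.1 and 5.7 use patient and implant interchangeably, and 48 per group with 80% power is valid only for independent units. Followed as written on implant rows, with one brand per patient and about two implants each, the regression of 5.8 has a true two-sided error of roughly 6% to 11% for ICC 0.1 to 0.5 with equal counts, and 8% to 19% at CV 0.8. Every ICC and CV is an assumption; only the mean of 2.08 implants per patient follows from the protocol, and that figure is a hope.

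Power falls clearly below 80% if 96 or 100 implants from fewer patients are accepted as the target. It falls slightly below (78%) in an implant-weighted analysis with a high ICC and widely varying counts. With 48 patients per arm and analysis of patient means, about 80% is the floor.

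**What to change.** - **5.7:** state the requirement as 48 patients per arm, 96 in total, with 5% loss included. Say that 80% power refers to a patient-level comparison of 0.2 mm with SD 0.34. If implant-level power is also quoted, give the assumed ICC, the implants per patient and their variation.
- **2 and 5.1:** give one agreed implant figure and label it as expected yield, not as the sample size.
- **5.5.1:** state one unit of allocation that fits the two patient groups of 5.1. The patient is randomised, all study implants of that patient are of the allocated brand, and the table is counted in patients. Replace the example block, which has 4 A and 6 B, with a balanced one.
- **5.8:** compare brands on patient means, or with a mixed model with a random patient intercept, or with GEE clustered by patient. If some enrolled patients already received both brands, record this and use the mixed model.

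The cost is wording in five sections and a patient-level allocation list for patients not yet allocated. No patients beyond the planned 96 and no new measurements are needed. If recruitment, planned from November 2022, has begun, an amendment should document how earlier patients were allocated.

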### 5.8.- Statistical analysis

The variable data will be entered into the Excel program of the Microsoft Office 2019 Package (Microsoft Corporation, Washington, USA, 2013) and will be analyzed with the SPSS 26.0 program for Windows (SPSS, Illinois, USA, 2019).

The data collected will be processed using the STATA 14.0 statistical package. A descriptive analysis of the qualitative and quantitative variables will be carried out. The Kolmogorov-Smirnov test will be used to analyze the normality of the measurements.

The relationship between bone loss and implant position will be analyzed using parametric t-test.

The level of statistical significance chosen is 5% ( $\alpha = 0.05$ ). To evaluate the association between the dependent variable bone loss from T0 to T2 and successive Ts and the independent variables implant A, Implant B placement, a multiple linear regression analysis will be used.

All variables considered to potentially affect the study relationship, such as sex, age, and smoking, will be used as control variables in the regression; the number of cigarettes per day, maxilla or mandible, ISQ [implant stability value] and contact of the mesial and distal implant (penseic ade dinets and/or implants by mesial and distal)

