## **1.- BACKGROUND OF THE SUBJECT**

Dental implants have been introduced as an option for replacing missing teeth, since the initial studies of [name] in the 1950s, there are multiple studies that support it, including (Andersson B, 1995; Arlin M, 1993; Noack et al, 1999; Jemt T, 2017; The accepted criteria for evaluating implant success were proposed by Albrektsson et al. (Albrektsson et al, 1986), who to identify clinical evidence of successful osseointegration and implant survival, suggested that a marginal bone loss of less than 1.5 mm in the first year and 0.2 mm in the following years, it is acceptable after implant loading (Díaz-Sánchez et al, 2019). Over the past three decades, implant success has been evaluated by survival rates, prosthesis stability, radiographic bone loss, and the absence of infection in the peri-implant soft tissues (Albrektsson et al, 1986; Smith and Zarb 1989; Buser et al, 1990, Albrektsson and Zarb 1998, Misch et al, 2008; The progressive knowledge of patients has increasingly required treatments that offer better aesthetics and comfort, making implantology a demanding field, where obtaining osseointegration or meeting the success criteria of implants highlighted by the lack of pain and infection, absence of radiolucency and mobility and possibility of restoration (Buser et al, in the 1990s). Thus, new parameters have been introduced to evaluate the long-term success of implant restorations. Including health status and natural-looking peri-implant soft tissues, prosthodontic parameters, aesthetics and patient satisfaction. However, osseointegration remains the predominant parameter in implantology (Furhauser et al, 2005; Meijer et al, 2005; Annibali et al, 2009; Belser et al, 2009).

Various authors describe that the position of the implant with respect to the crestal bone is a fundamental factor to preserve the bone in the future (Pontes et al, 2008; Novaes et al, 2009; De Siqueira et al, 2017; Wennerberb et al. al, 2003; Although, regarding this issue there continues to be controversy. Thus, some authors recommend placing the

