## **3- HYPOTHESIS**

### **3.1- Main hypothesis**

**Null hypothesis:** A brand of implant behaves in the same way in terms of marginal bone loss, if it is placed according to the indications specified by the manufacturer (crestal level or supracrestal level).

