### **4.2 Secondary objectives:**

- Relationship between marginal bone loss and suprabony soft tissue in mm.
- Relationship between marginal bone loss and ISQ value at the time of implantation.
- Relationship between marginal bone loss and torque (in Newton) at the time of implantation.
- Relationship between marginal bone loss and implant location.
- Relationship between marginal bone loss and the degree of periodontal disease.
- Relationship between marginal bone loss and systemic diseases.
- Relationship between marginal bone loss and smoking

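### Section 5.8 names an unadjusted t-test for bone loss by implant position without defining position; if it means anatomical site, or a level that varies within brand, the test is open to confounding

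*Protocol*

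**What the plan says.** Section 5.8 contains two analyses of bone loss.

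- **A t-test.** "The relationship between bone loss and implant position will be analyzed using parametric t-test". No groups are defined and no covariates are named.
- **A regression.** Its exposure is implant type: "the independent variables implant A, Implant B placement, a multiple linear regression analysis will be used". The control variables are sex, age and smoking, followed by "the number of cigarettes per day, maxilla or mandible, ISQ [implant stability value] and contact of the mesial and distal implant". Jaw is therefore in the model, but as a control variable.

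The secondary objectives in section 4.2 include "Relationship between marginal bone loss and implant location", again without categories. The word *position* does not appear there.

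Elsewhere *position* has a different sense. Section 1 speaks of "the position of the implant with respect to the crestal bone is a fundamental factor to preserve the bone in the future", which is vertical level. The second pair of hypotheses in section 3.1 concerns one brand and refers to level: "if it is placed according to the indications specified by the manufacturer (crestal level or supracrestal level".

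On allocation, section 5.5.1 says that patients "will be randomized using a randomization table of 10 in 10 implants" to receive one implant type or the other. Neither site nor level is allocated separately.

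**The concern.** The t-test sentence is a stated choice of method, yet a reader cannot tell which comparison it governs. The meaning decides whether the method is sound.

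Anatomical site follows from where a patient needs implants. Patients with implants in one region may therefore differ from the others in age, smoking or neighbouring teeth. Section 5.8 accepts that such variables may matter and adjusts the randomised brand comparison for them. For position, where randomisation may give no protection, it names a test with no adjustment.

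If position is site, an observed difference could reflect who receives implants there rather than the site. The t-test and the jaw coefficient from the regression could also disagree, and 5.8 does not say which one answers the location objective.

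**Working it through.** **Step 1: the plan's own figure.** Section 5.7 gives a difference of 0.2 mm, SD 0.34, two-sided alpha 0.05, beta 0.2 and 5% loss.

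- n per group = 2 × (0.34 × (1.96 + 0.8416) / 0.2)² = 45.37
- After 5% loss: 45.37 / 0.95 = 47.75, rounded up to 48

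The stated 48 per group reproduces. It belongs to the brand comparison. No figure is given for position or location, and this point changes no sample size, alpha or power.

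**Step 2: the possible meanings of position.**

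| Meaning | Textual support | Randomised? | Consequence for the t-test |
|---|---|---|---|
| Anatomical site | Objective on location (4.2); jaw in the regression (5.8) | No | Open to confounding |
| Level varying within a brand | One reading of the second hypotheses (3.1), which concern a single brand at crestal or supracrestal level | No | Open to confounding |
| Level that follows implant type | Placement by manufacturer's indication (3.1); one bone-level and one tissue-level product named in section 2 | Yes, through implant type | Close to the crude brand comparison; not confounded |

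The other sections do not settle the matter. Section 4.1 describes both brands as placed at bone level, while 5.1 (Study design) calls both tissue level.

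**Step 3: what confounding could do on the first two meanings.** The protocol gives no covariate effects and no imbalance by site, so the following only illustrates scale. Assumptions: SD 0.34 mm (5.7), an even split between two positions, independent implants, no true position effect, and a factor worth 0.2 mm of bone loss whose prevalence differs between positions by 10, 20 or 30 percentage points. The 0.2 mm and the prevalence differences are not from the protocol's data; 0.2 mm is simply borrowed from the difference in 5.7.

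- Bias = prevalence difference × 0.2 mm = 0.02, 0.04 or 0.06 mm
- SE = 2 × 0.34 / √N, which is 0.069 mm for N = 96 (5.7) and 0.048 mm for N = 200 (at least 100 per arm, 5.1 Study design)
- False-positive rate = P(|Z + bias/SE| > 1.96)

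| Bias (mm) | N = 96 | N = 200 |
|---|---|---|
| 0 | 5% | 5% |
| 0.02 | 6% | 7.0% |
| 0.04 | 9% | 13.2% |
| 0.06 | 14% | 23.9% |

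**Step 4: several implants per patient.** Section 5.1 (Study design) plans 96 patients and at least 100 implants per arm, so at least 200 / 96 ≈ 2.1 implants per patient. Neither the t-test nor the regression, as written, allows for this. The independence assumed in step 3 is therefore a simplification.

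**The case against.** The strongest reply is that position probably means vertical level. The background uses the word that way repeatedly, and the protocol has other terms for site: location, and maxilla or mandible. If level follows the manufacturer's indication, it follows the randomised implant type and the confounding argument falls away. That stands for that reading. It does not settle which reading applies, and it leaves the location objective without a named analysis of its own.

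Second, the planned regression already contains "the number of cigarettes per day, maxilla or mandible" and will yield an adjusted jaw coefficient. That is correct, and it makes the remedy cheap. But 5.8 does not say that this coefficient answers the location objective.

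Third, the objective is one of seven secondary relationships. An unadjusted association can be a legitimate description, and site categories are commonly left to a statistical analysis plan. This limits the weight of the point. It does not excuse a named test whose grouping variable is undefined.

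Four stronger readings are tempting and should not be drawn:

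- **That the location result is confounded.** The protocol gives neither the size nor the direction of any bias. The exclusions in 5.3 (heavier smokers, severe periodontal disease, uncontrolled diabetes) also limit some strong patient-level factors.
- **That the plan ranks the t-test above the regression.** Nothing in 5.8 does so.
- **That brand confounds site.** A randomised brand differs by site only by chance, unless allocation depends on site, which nothing states.
- **That a t-test cannot fit the data because it takes two groups.** The only site variable 5.8 names, jaw, has two levels. The limit matters only if finer categories are intended.

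**Conclusion.** The point holds in conditional form. The firm defect is that 5.8 ties a specific unadjusted test to an undefined variable. If position is anatomical site, or a level that varies within brand, the comparison is not randomised, the t-test is open to confounding by variables the section itself lists, and the adjusted estimate is the better answer. If level follows implant type, the t-test is not confounded, and the remaining gap is that location is covered only by a jaw control term.

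No size can be derived from the protocol. The rates of 6–14% (96 implants) and 7–24% (200 implants) rest wholly on the assumed factor effect, prevalence differences, even split and independence. The brand comparison and its sample size are unaffected. This is a modest correction to a secondary analysis.

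**What to change.** In section 5.8, state what position means, then:

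- **Location objective.** Report the adjusted maxilla/mandible coefficient from the regression already planned, or site categories with one overall test. Keep brand, age, sex, smoking and mesial/distal contact in the model, and use standard errors that allow for several implants per patient. Keep unadjusted site means as description only.
- **If position means a level that follows brand.** Keep that contrast and call it the brand comparison. Do not enter level beside brand in the same model, because the two would be largely collinear.
- **If position means a level that varies within brand.** Say so, and take its estimate from an adjusted model for the same reason as for site.

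The cost is a sentence or two in 5.8. Jaw is already a planned covariate and no new data are needed. The downside is a few degrees of freedom if more than two site categories are used.

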## **3- HYPOTHESIS**

### **3.1- Main hypothesis**

#### **Null hypothesis:**

Two different brands of implants behave in the same way in terms of marginal bone loss, if they are placed based on the indications specified by the manufacturer.

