## **4-OBJECTIVES**

### **4.1 Main objective:**

To evaluate marginal bone loss in two different brands of implants placed at the bone level.

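### Section 5.8 tests the two implants on bone loss over several undefined time points with no primary one, so the single comparison sized in 5.7 is not identified

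*Protocol*

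**What the plan says.** Section 5.8 makes the outcome of the multiple linear regression "the dependent variable bone loss from T0 to T2 and successive Ts", with implant A or B as the explanatory variable. The error rate is set once: "The level of statistical significance chosen is 5" per cent. The t-test in the same section has no time attached.

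T labels occur only in that sentence of 5.8. T0, T2 and the later Ts are not defined, and T1 is not mentioned. The sessions in 5.5 carry no T labels:

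- **5.5.3:** "A periapical X-Ray will be taken immediately after the surgery to control the marginal bone loss".
- **5.5.4:** clinical and radiographic measurements at 3 months (mandible) or 4 months (maxilla), each ±15 days, before prosthetic rehabilitation starts.
- **5.5.5:** reviews every 3 months ±15 days for 2 years after the prosthesis is placed. A radiograph at these reviews is not stated.

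Section 3.1 gives two null hypotheses, "Two different brands of implants behave in the same way in terms of marginal bone loss" and "A brand of implant behaves in the same way in terms of marginal bone loss", and neither names a time. The main objective in 4.1 is "To evaluate marginal bone loss in two different brands of implants placed at the bone level", again without a time. Section 5.7 reads "Accepting an alpha risk of 0.05 and a beta risk of 0.2 in a bilateral contrast", and says that 48 per group "are needed to detect a difference equal to or greater than 0.2 units". It assumes a common SD of 0.34 and 5% loss, and does not say at which time.

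**The concern.** A difference of 0.2 mm, an SD and a loss rate have meaning only at a stated time after a stated baseline. Section 5.7 fixes all three for one comparison, while 5.8 puts the brand question at more than one time without ranking them. The 5% and 80% therefore belong to a comparison that the protocol does not identify.

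The candidate times also measure different things. Change up to the osseointegration visit is change before prosthetic rehabilitation; change up to a later review includes the period after the prosthesis. The success criterion cited in 5.5.3 counts bone loss after loading, so the difference is material to this trial. If the brands differ at one visit and not at another, nothing in the protocol says which result answers the main question.

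**Working it through.** **1. Reproduce 5.7.** Inputs from 5.7: difference 0.2, SD 0.34, two-sided alpha 0.05 (z = 1.960), beta 0.2 (z = 0.842), loss 5%.

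n per group = 2 × ((1.960 + 0.842) × 0.34 / 0.2)² = 45.4. Allowing for loss: 45.4 / 0.95 = 47.8, rounded up to 48.

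The stated 48 is reproduced. It is the size for one comparison at one time, with the whole 5% spent on it.

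**2. Look for the time of that comparison.**

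| Place in protocol | Time given |
|---|---|
| 3.1 hypotheses | none |
| 4.1 main objective | none |
| 5.5.3 post-surgery radiograph | immediately after surgery, no T label |
| 5.5.4 osseointegration visit | 3 or 4 months ±15 days, no T label |
| 5.5.5 reviews | every 3 months for 2 years (24 / 3 = 8 reviews), no T label, no radiograph stated |
| 5.7 sample size | none |
| 5.8 analysis | T0, T2 and later Ts, undefined |

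No row links a T to a visit, and none marks a time as primary.

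**3. Illustrate what several co-equal times would do to the 5%.** Suppose each of k times is tested at two-sided 5%, there is no true difference, and the test statistics have equal correlation ρ. Then

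P(at least one |z| > 1.96) = 1 − ∫ φ(u) [Φ((1.96 − √ρ·u)/√(1−ρ)) − Φ((−1.96 − √ρ·u)/√(1−ρ))]^k du.

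Numerical integration gives:

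| k | ρ = 0.95 | ρ = 0.5 |
|---|---|---|
| 1 | 5.0% | 5.0% |
| 2 | 6.5% | 9.1% |
| 4 | 8.0% | 15.6% |

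Both k and ρ are assumptions. Testing each time separately at 5% is a natural reading of 5.8, but the section does not say it in so many words.

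**The case against.** **T2 may be the intended main time.** It is named first, and the sentence can be read as one main interval followed by later follow-up. If T0 is the post-surgery radiograph and the labels count radiographic measurements in order, the osseointegration visit would be T1 and T2 would fall after rehabilitation begins. This is a fair inference, but it is only that. Even if accepted, it does not say which later visit T2 is, and the sentence gives the later Ts the same standing.

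**The false-positive figures are hypothetical.** This stands. Section 5.8 never says that a result at any one time would count as a positive trial, and with a single test the error is 5%. The figures are illustrations.

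**A statistical analysis plan may settle this.** Visit labels, the ranking of later times and the handling of multiplicity are often left to such a plan, and none is shown. The figure in 5.5.6 is also not shown, and its caption refers to comparison at different times. But the protocol itself sets the outcome with undefined labels, and it sets the sample size without a time. The time of the primary outcome belongs with that calculation.

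**A reader might infer that the trial is too small.** Splitting 5% by Bonferroni over 2 or 4 times with 5.7's inputs would give 58 or 68 per group, or power of 71% or 62% at 48. The documents do not support that conclusion. Section 5.7 counts its 48 as implants, and 5.1 hopes for at least 100 implants per arm from 48 patients per group. With 100 × 0.95 = 95 evaluable implants per arm treated as independent, power at alpha 0.025 and 0.0125 is about 96% and 94%. At an assumed within-patient correlation of 0.5, the design effect is 1 + (100/48 − 1) × 0.5 = 1.54, the effective number is 95 / 1.54 = 61.6, and power is about 85% and 78%. The 71% and 62% return only at a correlation of 1. The 100 is a hope and the correlation is not given. The split is in any case not needed under the fix.

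**Conclusion.** The point holds as one of identification. The protocol analyses the brand comparison at several undefined times of equal standing, and the one comparison sized in 5.7 cannot be matched to any of them. This goes beyond missing detail, because it leaves the deciding visit open to choice after the data are seen.

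The arithmetic of 5.7 is correct, and sizing a trial on one comparison is normal practice; neither is a fault. Nor do the documents establish that the error rate will exceed 5% by any particular amount. The 6.5–9.1% (2 times) and 8.0–15.6% (4 times) show what could happen if each time were tested at 5%, for assumed correlations of 0.95 to 0.5. The point does not depend on them: even with a single T, the visit that answers the main question is unknown.

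This should be corrected. It does not by itself call for a larger trial.

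**What to change.** - In 5.5, map each T to a visit and its window.
- Name one primary change, from the immediate post-surgery radiograph (5.5.3) to one visit at which a radiograph is confirmed. Carry it into 3.1, 4.1 and 5.8, and test it once at two-sided 5%.
- In 5.7, state that 0.2 mm and SD 0.34 refer to that time, after checking the source study. If they do not, restate the calculation.
- Label all other times secondary and report them with confidence intervals. One repeated-measures model is a possible way to do this, not a requirement.

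**Cost.** The main conclusion then rests on one visit. The osseointegration visit (5.5.4) already has a radiographic measurement, so choosing it changes only wording, but it precedes rehabilitation and misses any loss during the 2 years after the prosthesis. A later review (5.5.5) covers that period, but the protocol must first confirm that a radiograph is taken there. Either way, 48 per group is unaffected by this change provided that 0.2 mm, SD 0.34 and 5% loss apply at the chosen time.
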